#### Exclusion of PK parameters

The ADS ADPP contains column variables APEXC and APEXCO indicating inclusion/exclusion (APEXC) of a PK parameter and an analysis flag comment (APEXCO). All analyses based on the PKS are based on PK parameter values which are not flagged for exclusion, i.e. with APEXC equal to "Included".

#### Exclusion of plasma concentrations

The ADS ADPC (PK concentrations per time-point or per time-interval) contains column variables ACEXC or ACEXCO indicating inclusion/exclusion (ACEXC) of a concentration and an analysis flag comment (ACEXCO). Exclusion of a concentration depends on the analysis flag comment ACEXCO. For example, if ACEXCO is set to "ALL CALC", the value will be excluded for all types of analyses based on concentrations. If ACEXCO is set to "DESC STATS" the value will be excluded from descriptive evaluations per planned time point/time interval. If ACEXCO contains the addition "TIME VIOLATION" or "TIME DEVIATION", the value can be used for further analyses based on actual times. If ACEXCO is set to "HALF LIFE", the value will be excluded from half-life calculation only; the value is included for all other analyses.

Further details are given in 001-MCS-36-472\_RD-01 "Noncompartmental Pharmacokinetic / Pharmacodynamic Analyses of Clinical Studies" ([5](#)) and 001-MCS-36-472\_RD-03 "Description of Analytical Transfer Files and PK/PD Data Files" ([6](#)).

## **7.5 SECONDARY ENDPOINT**

### **7.5.1 Key secondary endpoint**

Not applicable.

### **7.5.2 Secondary endpoint**

The secondary PK endpoint  $AUC_{0-\infty}$  will be analysed in the same way as described for the primary PK endpoint.

Descriptive analyses of the secondary PK endpoint will be performed according to BI standards ([5](#)) [001-MCS-36-472\_RD-01].

See [Section 7.4](#) of this TSAP for details regarding exclusion of PK parameters and plasma concentrations.

## **7.7 EXTENT OF EXPOSURE**

Only descriptive statistics are planned for this section of the CTR, see also [Section 7.3](#).

## **7.8 SAFETY ANALYSIS**

All safety analyses will be performed on the TS.

### **7.8.1 Adverse events**

AEs will be coded with the most recent version of MedDRA.

The analyses of AEs will be descriptive in nature. All analyses of AEs will be based on the number of subjects with AEs and not on the number of AEs.

For analysis, multiple AE occurrence data on the eCRF will be collapsed into one event provided that all of the following applies:

- All AE attributes are identical (lower level term, intensity, action taken, therapy required, seriousness, reason for seriousness, relationship, outcome, AESI)
- The occurrences were time-overlapping or time-adjacent (time-adjacency of two occurrences is given if the second occurrence started at most 1 hour after the first occurrence ended)

For further details on summarization of AE data, please refer to "Analysis and Presentation of Adverse Event Data from Clinical Trial" ([7](#)) [001-MCG-156] and "Handling of missing and incomplete AE dates" ([4](#)) [001-MCG-156\_RD-01].

The analysis of AEs will be based on the concept of treatment emergent AEs. That means that all AEs will be assigned to the screening phase or on-treatment phase as defined in [Section 6.1](#).

An overall summary of AEs will be presented. This overall summary will comprise summary statistics for the class of other significant AEs according to ICH E3 and for the class of AESIs.

**CTP:** *The AESI in this trial is hepatic injury, as defined by the following alterations of hepatic laboratory parameters:*

- *an elevation of AST and/or ALT  $\geq 3$ -fold ULN combined with an elevation of total bilirubin  $\geq 2$ -fold ULN measured in the same blood sample, and/or*
- *aminotransferase (ALT, and/or AST) elevations  $\geq 10$  fold ULN*

The investigator had to classify on the eCRF whether an observed AE was an AESI or not.

According to ICH E3 ([9](#)), AEs classified as "other significant" need to be reported and will include those non-serious and non-significant AEs

- (i) which are marked haematological or other lab abnormalities, or
- (ii) which were reported with "action taken = discontinuation" or "action taken = reduced", or
- (iii) which lead to significant concomitant therapy as identified by the Clinical Monitor/Investigator at a Medical Quality Review Meeting.

The frequency of subjects with AEs will be summarised by treatment, primary SOC and preferred term. AEs which were considered by the investigator to be drug related will be summarised separately. Separate tables will also be provided for subjects with SAEs, subjects with AESIs and subjects with other significant AEs (according to ICH E3 ([9](#))). The frequency of subjects with AEs and the frequency of subjects with AEs considered by the investigator to be drug related will also be summarised by maximum intensity, primary SOC and preferred term.

The SOCs and preferred terms within SOCs will be sorted by descending frequency overall treatment groups.

For disclosure of AE data on ClinicalTrials.gov, the frequency of subjects with non-serious AEs occurring with an incidence of greater than 5 % (in preferred terms) will be summarised by treatment, primary SOC and preferred term. The frequency of subjects with SAEs will also be summarised.

For disclosure of AE data in the EudraCT register, the frequency of AEs, the frequency of non-serious AEs with an incidence of greater than 5 % (in preferred terms) and the frequency of SAEs will be summarised.

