12. EOT (End of trial examination) includes physical examination, body weight, vital signs, ECG, safety laboratory, recording of AEs and concomitant therapies. EOT to be performed not before last PK and ADA sampling.
13. Safety laboratory is to be taken within two days prior to study drug administration and can be omitted if the screening examination is performed between Day -5 and Day -3.
14. First measure after completion of infusion is the collection of PK sample
15. In case plasma levels still exceed LOQ additional PK samples may be collected beyond Day 176 ±3.

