#### Safety and tolerability

In the FIH study [[c09985235-01](#)], 49 of 78 subjects (62.8%) reported at least 1 treatment-emergent AE (TEAE). This included 36 of 58 subjects (62.1%) following administration of BI 655130 and 13 of 20 subjects (65.0%) following administration of placebo. There was no apparent relationship between the frequency of AEs and the dose. AEs categorised as related to treatment were observed in 3/20 (15.0%) subjects in the placebo group and in 8/58 (13.8%) subjects treated with BI 655130.

Treatment-emergent AEs were reported most frequently in the system organ classes 'infections and infestations' (BI 655130: 14/58 subjects [24.1%]; placebo: 3/20 subjects [15.0%]), 'general disorders and administration site conditions' (BI 655130: 9/58 subjects

Proprietary confidential information © 2017 Boehringer Ingelheim International GmbH or one or more of its affiliated companies

[15.5%]; placebo: 2/20 subjects [10.0%]), 'gastrointestinal disorders' (BI 655130: 7/58 subjects [12.1%]; placebo: 4/20 subjects [20.0%]), 'musculoskeletal and connective tissue disorders' (BI 655130: 5/58 subjects [8.6%]; placebo: 3/20 subjects [15.0%]), and 'nervous system disorders' (BI 655130: 5/58 subjects [8.6%]; placebo: 3/20 subjects [15.0%]).

At preferred term level, the most frequently reported treatment-emergent AEs were nasopharyngitis (BI 655130: 12/58 subjects [20.7%]; placebo: 3/20 subjects [15.0%]), headache (BI 655130: 5/58 subjects [8.6%]; placebo: 3/20 subjects [15.0%]), influenza like illness (BI 655130: 4/58 subjects [6.9%]; placebo: 2/20 subjects [10.0%]), and diarrhoea (BI 655130: 2/58 subjects [3.4%]; placebo: 2/20 subjects [10.0%]).

There were two AEs of moderate intensity, both considered non related to the study drug, (injection site hematoma, headache); all remaining AEs were of mild intensity.

There were no relevant changes compared to placebo for laboratory safety, including clinical chemistry, hematology, coagulation parameters, and urinalysis. No clinically relevant changes were observed in 12 lead ECGs, vital signs, physical exams and cardio-monitoring.

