- Careful dose selection based on data from the completed FIH study; the exposure of any dose of BI 655130 in the current study is projected to be below the highest exposure observed in the FIH study
- For safety reasons, the study will start with the lowest SC dose of \_\_\_\_\_ of BI 655130. The dose group will be divided into 2 cohorts: on the first study day, 6 subjects will be treated, with an interval between the injections of at least 15 min. The second cohort will be treated at least 48 h apart. There will be an interval of at least 1 week after the first dosing in the \_\_\_\_\_ SC dose group before the start of the SC or IV dose groups in a randomised sequence (in one week 6 subjects on IV and 6 subjects on SC and in the following week again 6 + 6) No more than 2 subjects should simultaneously receive an infusion. At any time during the ongoing study, further dosing will be stopped in case of safety and tolerability concerns based on the criteria defined in [Section 3.1](#)
- Dose escalation will be shallow (2-fold dose escalation step). In addition, a time interval of at least 7 days will be maintained between the first dosing of \_\_\_\_\_ of BI 655130 SC and the first dosing of \_\_\_\_\_ of BI 655130 SC or IV. An interval of one week between the dose groups is expected to cover the period of highest risk / peak effect. The decision to proceed to the next dose will be based upon the safety and tolerability of the preceding dose. The next dose will only be given if no safety concerns arise in the previous dose group (i.e. no dose-limiting events occur) and if none of the pre-specified trial-specific stopping criteria are met (see [Section 3.3](#)).
- The dose will only be escalated if previously approved by the Principal Investigator (or an authorised deputy) and the trial clinical monitor (or an authorised deputy) after in-depth analysis of all available safety data (see [Section 3.1](#))
- Monitoring of ECG and vital signs is incorporated, with continuous ECG monitoring over 1.5 hour post dose after each drug administration, the anticipated period of highest drug exposure. As an additional measure, repeated single 12-lead ECGs are scheduled in the further course of the study. The rationale for the intensified ECG monitoring is not an expected increased risk of BI 655130 mediated effects on cardiac repolarization
- Extensive safety laboratory testing will be performed ([Table 5.2.3:1](#))

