## **3.2      DISCUSSION OF TRIAL DESIGN, INCLUDING THE CHOICE OF CONTROL GROUP**

The trial will be conducted open-label. Blinding is not possible because the treatments are distinguishable. The open-label treatment is not expected to bias results, since the relative bioavailability endpoints are derived from measurement of plasma concentrations of the analyte.

For safety reasons, the trial will be conducted in a fixed sequence; a time interval of at least 7 days will be maintained between the first dosing of                    of BI 655130 SC and the first dosing of                    of BI 655130 SC or IV.

Proprietary confidential information © 2017 Boehringer Ingelheim International GmbH or one or more of its affiliated companies

No placebo group is included because the study is open-label with a focus on PK. Local tolerability is an additional objective and will remain relevant in case of dose limiting local AEs, whether placebo controlled or not. The systemic AEs have been evaluated up to MRD, a far higher dose than planned for the current study.

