The REP for BI 655130, when measurable drug levels or PD effects are still likely to be present after the last administration, is not known at this early stage of development. Therefore, all AEs reported until the end of trial examination will be considered on treatment; please see [Section 7.3.3](#).

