### **7.3.3 Safety analyses**

Safety will be assessed for the endpoints listed in [Section 5.2.1](#). All treated subjects (that is, all subjects who received one dose of study drug), will be included in the safety analysis. Safety analyses will be descriptive in nature and will be based on BI standards. No hypothesis testing is planned.

The analyses will be done by 'treatment at onset'.

Treatments will be compared in a descriptive way. Tabulations of frequencies/proportions will be used for the evaluation of categorical (qualitative) data, and tabulations of descriptive statistics will be used to analyse continuous (quantitative) data.

Measurements (such as ECG, vital signs, or laboratory parameters) or AEs will be assigned to treatments (see [Section 4.1](#)) based on the actual treatment at the planned time of the measurement or on the recorded time of AE onset (concept of treatment emergent AEs).

Therefore, measurements planned or AEs recorded prior to administration of trial medication will be assigned to 'screening', those between trial medication administration until the end of trial visit will be assigned to the treatment period, and those after the end of trial examination will be assigned to 'post-study'. These assignments including the corresponding time intervals will be defined in detail in the TSAP.

Additionally, further treatment intervals (analysing treatments) may be defined in order to provide summary statistics for time intervals, such as combined treatments, on-treatment totals or periods without treatment effects (such as screening and post-study intervals).

Adverse events will be coded using the Medical Dictionary for Regulatory Activities (MedDRA). Frequency, severity and causal relationship of AEs will be tabulated by treatment, system organ class and preferred term. SAEs, AESIs (see [Section 5.2.2.1](#)) and other significant AEs (according to ICH E3) will be listed separately.

Laboratory data will be compared to their reference ranges. Values outside the reference range as well as values defined as clinically relevant will be highlighted in the listings. Additionally, differences from baseline will be evaluated. Measurements taken immediately prior to drug administration on Day 1 will be considered as baseline values.

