## **6. GENERAL ANALYSIS DEFINITIONS**

### **6.1 TREATMENTS**

For basic study information on treatments to be administered, assignments of dose groups, and selection of doses, cf. Section 4 of the CTP.

Subjects were planned to be treated either with one single dose of

- as subcutaneous (SC) injection (exploratory reference treatment (ER))  
or
- as intravenous (IV) infusion (reference treatment (R))  
or
- as SC injection (test treatment (T)).

For statistical analysis of AEs, safety laboratory data and vital signs, the following analysis phases are defined for each subject:

Table 6.1: 1 Flow chart of analysis phases for statistical analyses of AEs, safety laboratory data and vital signs

Study analysis phase	Label	Start (inclusive)	End (exclusive)
Screening	Screening	Date of informed consent	Date/time of administration of study drug
On-treatment	BI SC, or BI IV or BI SC, respectively	Date/time of administration of study drug	0:00 AM on day after subject's trial termination date

CTR Section 15, Appendix 16.1.9.2.8.2 and Appendix 16.1.9.2.8.3 AE displays will present results for the on-treatment phase only.

In CTR Section 15 AE tables (but not in Appendix 16.1.9.2.8.2 and Appendix 16.1.9.2.8.3 AE tables), the following total will be provided in addition:

- "**Total on-trt BI**", defined as the total over all on-treatment phases involving BI 655130

CTR Appendix 16.1.9.2.8.1 displays will present results for the screening and on-treatment phases.

Additionally to the totals defined above, the following total will be provided in CTR Section 16.1.9.2.8.1 AE tables:

- "**Total**", defined as the total over all study phases (incl. screening and on-treatment).

More details on the technical implementation of these analyses are provided in the ADS Plan of this TSAP.

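### AE tables pool about 25 weeks into one on-treatment phase with no split by onset, which dilutes an acute difference between groups, most of all in the any-AE summary

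*SAP*

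**What the plan says.** SAP 7.8.1 bases the AE analysis on treatment emergence: "all AEs will be assigned to the screening phase or on-treatment phase as defined in" SAP 6.1. Table 6.1: 1 there has two phases, screening and on-treatment. The second starts at drug administration and ends at "0:00 AM on day after subject's trial termination date". The Flow Chart puts the end-of-trial visit at Day 176 ±3 (4200 h), not before the last PK sample. Because "additional PK samples may be collected beyond Day 176 ±3", the phase may be longer for some subjects.

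The long phase comes from the protocol. Section 5.2.2.2 says that the residual effect period is unknown, so "all AEs reported until the end of trial examination will be considered on treatment". Protocol 7.3.3 also leaves room to subdivide: "further treatment intervals (analysing treatments) may be defined in order to provide summary statistics for time intervals". The SAP defines no interval within the on-treatment phase.

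SAP 7.8.1 counts subjects with AEs, not events. It plans tables by SOC and preferred term for all AEs, the same for drug-related AEs, and both by maximum intensity. None is by time of onset. SAP 7.8.6 summarises local tolerability overall and by time point, but the Flow Chart (note 5) restricts that assessment to SC subjects. Protocol 3.2 states "No placebo group is included because the study is open-label with a focus on PK". Protocol 5.2.2.2 requires onset time to be recorded for every AE.

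**The concern.** Safety and tolerability are an additional objective (Protocol 2.2), judged by describing three groups of 12. When each subject counts once over 25 weeks, a headache two hours after dosing and a cold on Day 170 contribute equally. A subject who will have some background illness anyway adds nothing to the any-AE row by also having an early reaction. As the background proportion nears 100%, the row loses its ability to show an acute difference between routes or doses.

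The background in this programme is not small: "13 of 20 subjects (65.0%) following administration of placebo" had at least one AE in the first-in-human trial. With no placebo group here, timing relative to the dose helps to separate acute reactions from background, and it depends less on judgement than an open-label causality assessment. The planned tables do not use it.

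**Working it through.** **Inputs from the documents.** Follow-up: 4200 h / 24 / 7 = 25.0 weeks. Any-AE rate on placebo: 13/20 = 65.0% (first-in-human trial) and 87.5% (multiple-dose trial; 7/8 with 8 placebo subjects). Drug-related AE rate on placebo: 3/20 = 15.0% (first-in-human trial). Nasopharyngitis and headache on placebo in that trial: also 3/20 each. Group size: 12. The documents contain no design calculation for AEs to reproduce.

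**Assumptions.** The AE observation window behind those rates is not stated. I vary it over T0 = 4, 10 and 25 weeks; 10 weeks is the central case only because the biomarker time course of the first-in-human trial ran to 1680 h. The background hazard is constant. One group has an additional, independent chance e = 1/3 of an AE in week 1. The value of e is illustrative.

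**Formulas.** Background over T weeks: b(T) = 1 − (1 − p)^(T/T0). Affected group: s(T) = 1 − (1 − b(T))(1 − e). From two independent binomials with n = 12, compute the chance that the affected group shows at least 3 more subjects with an AE.

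**Central case, any AE.**
- Pooled: b = 1 − 0.35^2.5 = 92.8%; s = 1 − 0.0725 × 2/3 = 95.2%. The gap is 2.4 points, or 0.3 of 12 subjects.
- Week 1: b = 1 − 0.35^0.1 = 10.0%; s = 1 − 0.900 × 2/3 = 40.0%. The gap is 30 points, or 3.6 of 12 subjects.

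**Results.** The last column sets e = 0, so it is the chance of the same apparent excess with no drug effect.

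| Row (placebo rate) | T0, weeks | Background, pooled / week 1 | Chance of ≥3 more, pooled / week 1 | Same chance if e = 0, pooled / week 1 |
|---|---|---|---|---|
| Any AE (65%) | 4 | 99.9% / 23.1% | 0% / 61% | 0% / 11% |
| Any AE (65%) | 10 | 92.8% / 10.0% | 3% / 71% | 2% / 4% |
| Any AE (65%) | 25 | 65.0% / 4.1% | 31% / 77% | 14% / 1% |
| Any AE (87.5%) | 4 | 100.0% / 40.5% | 0% / 49% | 0% / 15% |
| Any AE (87.5%) | 25 | 87.5% / 8.0% | 9% / 73% | 6% / 3% |
| Drug-related, or a term at 15% | 4 | 63.8% / 4.0% | 32% / 77% | 14% / 1% |
| Drug-related, or a term at 15% | 10 | 33.4% / 1.6% | 53% / 80% | 14% / 0% |
| Drug-related, or a term at 15% | 25 | 15.0% / 0.6% | 67% / 81% | 7% / 0% |

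A preferred term with no background gives 82% over either window. In the central case the pooled any-AE row behaves almost the same with and without a drug effect (3% against 2%).

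**Sensitivity of week 1.** If week-1 background is 20% or 40% instead of 10%, the any-AE chance falls from 71% to 63% or 49%.

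**The case against.** A reader might infer that background illness hides any acute difference. The documents do not support that. The any-AE row is the most saturated one planned. On the same assumptions the drug-related table and a 15%-background preferred term keep a 53% chance (32% to 67%), and a distinctive term with almost no background keeps 82%. SC local tolerability, the aspect of tolerability that Protocol 2.1 singles out, is shown by time point, and laboratory values and vital signs are summarised over time. Onset is therefore not the only internal control. Two limits remain: causality is judged open-label, and the local data have no IV counterpart.

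A reader might also infer that the long phase is a mistake or departs from the protocol. It does neither. The residual effect period is unknown, the half-life in the higher dose groups of the first-in-human trial was 20.4 to 33.9 days, and the protocol option for further intervals is permissive. The statement that "An interval of one week between the dose groups is expected to cover the period of highest risk / peak effect" justifies spacing between dose groups; it does not define an AE analysis window. It is only a convenient anchor for one.

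The size of the effect is projected, not observed. The source AE windows are missing, the exact 95% interval for 13/20 is 40.8% to 84.6%, and AE queries are denser up to Day 8 than later, so a constant hazard is doubtful. With 12 per group an early table is no strong detector either: as a yardstick, two-sided 5% Fisher power in week 1 (central case) is 19% for a 30% excess and 53% for a 50% excess. No AE testing is planned. The higher SC and IV groups are dosed in the same weeks with the same follow-up, so the background dilutes their contrast and does not bias it.

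Finally, the analysis dataset plan and the company AE standard cited by the SAP are not in the documents. An onset display there cannot be excluded, and the listings would let a reader examine timing subject by subject.

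**Conclusion.** The point holds as one of dilution. A single 25-week on-treatment phase, subject-level counting, no placebo group and no onset split together make the any-AE summary a poor place to see an acute difference between SC and IV or between SC doses. The drug-related table and common preferred terms are partly diluted. Low-background terms and SC local tolerability by time point are little affected.

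In every scenario tried, the week-1 window shows the assumed excess more often than the pooled one where there is background to dilute it. The amount depends on the unstated source window, the constant hazard and the assumed one-third excess, so the percentages are illustrations. Priority is modest, between optional and recommended: safety is descriptive and an additional objective, and the primary bioavailability analysis is untouched.

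**What to change.** Keep the whole-period AE tables. In SAP 6.1 and 7.8.1 add, under the Protocol 7.3.3 option, the overall AE summary and the SOC and preferred-term tables (all AEs and drug-related AEs) by treatment for two onset intervals: from dosing to under 168 h, and from 168 h to end of trial. State that acute tolerability across routes and doses will be read from the first interval alongside the whole-period tables, descriptively. If the company standard or the analysis dataset plan already provides an onset display, cite it in SAP 7.8.1 instead.

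The cost is some SAP wording and a few extra tables from onset times already collected. The tables will have small counts, and late reactions will fall in the second interval, which is a further reason to retain the whole-period view.
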